8.3.6 Management of Adverse Events of Special Interest

Adverse events of special interest (AESIs) are serious or nonserious AEs that are of clinical interest and should be closely followed.

For this study, AESIs include only the following:

- Infusion-related reactions including immediate hypersensitivity.
- Immune-related adverse events.
- TGF β inhibition mediated skin reactions.
- Anemia.
- Bleeding AEs.

8.3.6.1 Infusion-related Reactions Including Immediate Hypersensitivity

Infusion-related reactions, including immediate hypersensitivity, are defined in this section. IRRs are AESIs and identified risks for bintrafusp alfa.

Infusion-Related Reactions

Infusion-related reactions are signs or symptoms experienced by participants during study intervention administration or within 1 day thereafter. An assessment for possible IRR should be triggered based on the clinical picture and temporal relationship to drug administration.

Possible IRRs are defined based on following 2 lists of Medical Dictionary for Regulatory Activities (MedDRA) Preferred Terms (PTs) and temporal relationship criteria. Events are divided into reactions versus signs and symptoms:

- Reactions include the PTs Infusion-Related Reaction, Drug-Hypersensitivity, Hypersensitivity, Type-1-Hypersensitivity and Anaphylactic Reaction. These PTs should be considered when onset is during the infusion or within 1 day thereafter.
- Signs and symptoms of infusion-related reactions include the PTs Pyrexia, Chills, Flushing, Hypotension, Dyspnea, Wheezing, Back Pain, Abdominal Pain and Urticaria. These PTs should be considered, if the onset occurs during or within 1 day after an infusion and resolves within 2 days.

Management of Infusion-Related Reactions

Current experience in more than 700 study participants revealed that IRRs to bintrafusp alfa occur seldomly and are generally mild to moderate in severity. Therefore, administration of a premedication is generally not required.

If an investigator deems necessary to administer a premedication prior to bintrafusp alfa infusion to a particular participant, an antihistamine (e.g., 25 to 50 mg diphenhydramine) and paracetamol (acetaminophen, 500 to 650 mg intravenously or equivalent oral dose) is recommended.

Premedication should be administered based upon clinical judgment and presence/severity of prior infusion reactions. This regimen may be modified based on local treatment standards and guidelines as appropriate provided it does not include systemic glucocorticoids.

Management of symptoms should follow the guidelines shown in [Table 5](#).

Table 5 Treatment Modification Guidance for Symptoms of Infusion-Related Reactions Including Immediate Hypersensitivity

NCI-CTCAE v5.0 Grade	Treatment Modification
Grade 1 – mild Mild transient reaction: in general, infusion interruption not indicated; intervention not indicated.	Increase monitoring of vital signs as medically indicated as participants are deemed medically stable by the attending Investigator. Hold infusion if deemed necessary by the Investigator.
Grade 2 – moderate Therapy or infusion interruption indicated but responds promptly to symptomatic treatment (e.g., antihistamines, NSAIDs, narcotics, IV fluids); prophylactic medications indicated for ≤ 24 hours.	Stop the infusion of the study intervention Increase monitoring of vital signs as medically indicated as participants are deemed medically stable by the attending Investigator. If symptoms resolve quickly, resume infusion at 50% of original rate with close monitoring of any worsening otherwise dosing held until resolution of symptoms with mandated premedication for the next scheduled visit. If not improving, consider administration of glucocorticoids and stop the infusion for that day. If the participant has a second IRR Grade ≥ 2 on the slower infusion rate despite premedication, the infusion should be stopped and the investigator may consider withdrawal of this participant from the study.
Grade 3 or Grade 4 – severe or life-threatening Grade 3: Prolonged (e.g., not rapidly responsive to symptomatic medication and/or brief interruption of infusion); recurrence of symptoms following initial improvement; hospitalization indicated for clinical sequelae. Grade 4: Life-threatening consequences; urgent intervention indicated.	Stop the infusion of study intervention- immediately and disconnect infusion tubing from the participant with additional appropriate medical measures and closely monitor until deemed medically stable by the attending Investigator. Hospitalization and/or close monitoring is recommended. Administration of glucocorticoids may be required For Grade 3 or 4 IRRs, permanent discontinuation of study intervention is mandated.
Once the infusion is interrupted or rate reduced to 50% of previous infusion rate, it must remain decreased for all subsequent infusions. For all types and grades of infusion reactions, details about drug physical constitution, method of preparation, and infusion must be recorded. Participants should be instructed to report any delayed reaction immediately.	

IRR=infusion-related reactions, IV=intravenous, NCI-CTCAE=National Cancer Institute-Common Terminology Criteria for Adverse Event, NSAIDs=nonsteroidal anti-inflammatory drugs.

Immediate Hypersensitivity Reaction

Hypersensitivity reactions may require immediate intensive care. Bintrafusp alfa should be administered in a setting that allows immediate access to an intensive care unit or equivalent environment and administration of therapy for anaphylaxis, such as the ability to implement immediate resuscitation measures. Potent steroids (e.g., dexamethasone), catecholamines (e.g.

epinephrine), allergy medications (IV antihistamines), bronchodilators, or equivalents and oxygen should be available for immediate access.

A complete guideline for the emergency treatment of anaphylactic reactions according to the Working Group of the Resuscitation Council United Kingdom and can be found at <https://www.resus.org.uk/pages/reaction.pdf>.

Flu-Like Symptoms

Treatment is based on clinical assessment and at the discretion of the Investigator. For prophylaxis of flu like symptoms, a nonsteroidal anti-inflammatory drug (NSAID), e.g., ibuprofen 400 mg or comparable NSAID dose, may be administered 2 hours before and 8 hours after the start of each IV infusion.

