15.2 Adverse Events

Treatment-emergent adverse events (TEAE) are those events with onset or worsening (seriousness or severity) dates occurring within the on-treatment periods as defined in Section 9.7.

For immune-related AEs, an extended period of up to 90 days after last treatment is considered for analyses dedicated to irAEs. PTs belonging to irAEs will be considered as treatment-emergent up to 90 days for dedicated irAE analyses and up to 30 days for general AE analyses.

This includes also AEs ongoing at baseline, which first improve under study intervention and then worsen irrespective of baseline. Adverse events with changes in toxicity grade/severity, seriousness or outcome of AEs are recorded as separate entries in the eCRF with associated end and start dates. Records of the same AE will be considered as one event in the analysis. If the severity of the reported event worsens after start of treatment, the TEAE flag will be re-evaluated for the worse and the subsequent records as per the TEAE definition. If the worse record starts outside of the on-treatment period, it will not appear on the summaries/listings of TEAEs, unless otherwise specified. These events will be kept as separate records in the database in order to maintain the full detailed history of the events. The overall outcome of the adverse event is the

outcome of the last event in the sequence. When such AEs are listed, start, end date and outcome should be provided together with change date, toxicity grade/severity and seriousness per episode.

Adverse events related to study intervention are those events with relationship missing, unknown or yes.

Immune-Related Adverse Events (irAE) are identified according to the methodology outlined in Appendix 1 for a pre-specified search list of MedDRA PTs, documented in the Benefit Risk Strategy Document. Prior to DB lock these events are identified according to a pre-specified search list of MedDRA PTs, documented in a version-controlled repository maintained by the Sponsor and based on medical assessment prior to analysis of the current study. Details are included in Appendix 1.

Infusion-Related Reactions (IRR) are identified based on a list of MedDRA PTs. The detailed criteria of the timing relationship to infusions are specified in [Table 1](#) of Appendix 1.

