15.3.3 Other Significant Adverse Events

The frequency (number and percentage) of participants with each of the following adverse events of special interest (AESIs) will be presented per indication or per parent protocol of the corresponding parent study.

The following AESIs will be presented by worst grade (Any grade [including missing grade], Grade \geq 3, Grade \geq 4, Grade 5):

- irAEs.

irAEs will be summarized in frequency tables presenting category, subcategory and sub-subcategory (if applicable) and PT sorted by alphabetical order.

- IRRs.

IRR AEs will be summarized overall and by subcategories (Reactions / Signs and Symptoms) in a frequency table presenting SOC and PT sorted by alphabetical order.

- TGF β inhibition mediated skin reactions.

TGF β inhibition mediated skin reactions will be summarized by PT categories (Narrow definition, Broad definition) and by PT sorted by alphabetical order.

- Anemia.

Anemia TEAEs and related anemia TEAEs will be summarized in a frequency table presenting SOC and PT sorted by alphabetical order.

In addition, bleeding TEAEs will be presented by worst grade (Any grade [including missing grade], Grade 1, Grade 2, Grade 3, Grade 4, Grade 5):

- Bleeding TEAEs.

Bleeding TEAEs and related bleeding TEAEs will be summarized in a frequency table presenting SOC and PT sorted by alphabetical order.

Details of AESIs are specified in Appendix 1.

AEs associated to COVID-19

A listing comprising all COVID-19 related AE terms will be presented. The relevant events will be identified based on the SMQ COVID-19 (narrow scope).

AEs associated to COVID-19 vaccines

The safety profile of the investigational treatment and vaccine may overlap. Investigators are asked to provide all AEs with potential COVID-19 vaccine related causality AEs as part of information on “Causality factors other than study treatment” and to enter “COVID19 vaccination” as free text on the AEDT eCRF page. Per this classification a focused analysis will be possible for potential vaccination associated AEs.

A listing comprising all COVID-19 vaccines related AE terms will be presented.

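### The 2-day resolution limit on infusion-reaction signs and symptoms makes inclusion depend on outcome, so severe infusion-reaction rows can be undercounted

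*Protocol*

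**What the plan says.** Protocol Section 8.3.6.1 opens by describing IRRs as signs or symptoms that arise while the drug is being given or in the day after. It then makes this operational: "Possible IRRs are defined based on following 2 lists of Medical Dictionary for Regulatory Activities (MedDRA) Preferred Terms (PTs) and temporal relationship criteria".

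- **Reactions list.** "Reactions include the PTs Infusion-Related Reaction, Drug-Hypersensitivity, Hypersensitivity, Type-1-Hypersensitivity and Anaphylactic Reaction". The timing rule is: "These PTs should be considered when onset is during the infusion or within 1 day thereafter". Nothing is said about when the event must end.
- **Signs-and-symptoms list** (pyrexia, chills, flushing, hypotension, dyspnea, wheezing, back pain, abdominal pain, urticaria). The timing rule is: "These PTs should be considered, if the onset occurs during or within 1 day after an infusion and resolves within 2 days".

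Table 5 in the same section describes severity. Its Grade 3 entry begins: "Grade 3: Prolonged (e.g., not rapidly responsive to symptomatic medication and/or brief interruption of infusion". It continues with symptoms that return after first improving and with hospitalization for sequelae. The table stops at Grade 4.

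SAP Section 15.3.3 reports IRRs by worst grade (any, 3 or higher, 4 or higher, 5) and states: "IRR AEs will be summarized overall and by subcategories (Reactions / Signs and Symptoms) in a frequency table". SAP Section 15.2.1 also carries IRRs and related IRRs in the overall adverse event summary. For the exact rule, SAP Section 15.2 says: "The detailed criteria of the timing relationship to infusions are specified in" Table 1 of Appendix 1. That appendix is blacked out in the public copy.

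**The concern.** Whether a sign or symptom counts as an IRR should depend on what it is and when it began relative to the infusion. Under the protocol rule it also depends on how the event turned out. Table 5 treats slow response and recurrence as marks of severity, so a ceiling on duration tends to remove the severe events more than the mild ones. An infusion-day hypotension that settles in an hour is counted. One that lasts three days, or never resolves, is not.

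IRRs are one of five adverse events of special interest in a study whose primary objective is safety. An empty Grade 5 cell, or a low Grade 3 or higher row, in the Signs and Symptoms block would be read as an observation when it may partly reflect the inclusion rule. Table 5 requires permanent discontinuation for Grade 3 or 4 IRRs, so a participant could be handled clinically as having a Grade 3 IRR and yet be absent from the IRR table.

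**Working it through.** The plan gives no figure to reproduce: IRRs are summarised descriptively and no IRR rate is stated. The check is to apply the two rules to each kind of event and map the result to the SAP's cells.

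**Step 1. Apply the rules to events with onset in the window** (during the infusion or within 1 day after).

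| List | Resolved within 2 days | Longer than 2 days, or ongoing | Fatal |
|---|---|---|---|
| Signs and symptoms | counted | not counted | not counted, if resolution is read literally |
| Reactions | counted | counted | counted |

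The fatal entry in the first row follows from Protocol Appendix 4: when an event leads to death, fatal is recorded as the outcome of that event, so it does not resolve.

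**Step 2. Map to the grade rows in SAP Section 15.3.3.**

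| Row | Signs and Symptoms | Reactions | Overall IRR |
|---|---|---|---|
| Grade 5 | empty on a literal reading | not constrained | not zero by construction, but misses fatal signs and symptoms |
| Grade 4 or higher | can be undercounted | unaffected | can be undercounted |
| Grade 3 or higher | can be undercounted | unaffected | can be undercounted |

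The last two rows are not forced to zero, because a Grade 3 or 4 symptom can resolve within 2 days. The overall rows change only if the participant has no other counted IRR of that grade.

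**Step 3. What one excluded event does.** Protocol Section 1.1 expects at least 10 participants. The IRR tables are produced per indication or per parent protocol and the group sizes are not given, so I assume 10 and, as a smaller case, 5. The plan does not call for these intervals; they only show scale. Exact (Clopper-Pearson) 95% limits:

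- 0/n: upper limit = 1 − 0.025^(1/n). For n = 10, 30.8%. For n = 5, 52.2%.
- 1/n: lower limit = 1 − 0.975^(1/n). For n = 10, 0.3%. For n = 5, 0.5%. The upper limit solves (1 − p)^n + np(1 − p)^(n−1) = 0.025. For n = 10, 44.5%. For n = 5, 71.6%.

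| Group size | Event counted | Event excluded |
|---|---|---|
| 10 | 1/10 = 10% (0.3% to 44.5%) | 0/10 = 0% (0% to 30.8%) |
| 5 | 1/5 = 20% (0.5% to 71.6%) | 0/5 = 0% (0% to 52.2%) |

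This is the effect of reclassifying any single event. It is not an estimate of how often that will happen.

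**Step 4. What dropping the limit would let in.** If the onset window is taken as the infusion day plus the next day (2 days, an assumption), it covers 2/14 = 14% of days on 2-weekly dosing and 2/21 = 10% on 3-weekly dosing. Dyspnea, pain or fever from the cancer itself would start in that window now and then by chance.

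**The case against.** Several stronger readings are tempting, and the documents do not support them.

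- **That the IRR Grade 5 cell as a whole is zero by construction.** It is not. A fatal anaphylactic, hypersensitivity or infusion-related reaction is counted through the Reactions list. Only the Signs and Symptoms cell is affected.
- **That every Table 5 Grade 3 reaction drops out.** Table 5 ties prolongation to poor response to medication or interruption and gives no number of days. The filter acts on duration, not grade: a severe symptom over in 2 days stays, and a mild back pain lasting three days goes.
- **That Table 5 grades fatal reactions as severe.** It has no fatal category.
- **That the primary endpoint is biased.** That endpoint is occurrence of adverse events and treatment-related adverse events. An excluded event that is treatment-emergent still appears by system organ class, preferred term and worst grade, in the serious event tables if serious, in the death outputs if fatal, and in the listing of all adverse events. What it loses is the IRR label, and the visible text of those outputs does not restore the link to infusion timing.

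Four further arguments carry weight. First, Appendix 4 asks for the diagnosis to be recorded in place of its component symptoms where possible, so some severe reactions will be coded to the Reactions list. The symptom list, however, exists for the events that are not. Second, the SAP's operative rule is unseen. If resolution is programmed as an end date within 2 days, a death inside that window could be counted. Third, the SAP's Safety Analysis Set requires a dose in the rollover study, so a fatal IRR could arise only from a rollover infusion, and the protocol describes IRRs as infrequent and mostly mild to moderate. Fourth, the limit plausibly serves specificity, as Step 4 shows. For that reason, counting all Grade 3 or higher listed terms as IRRs would exchange one distortion for another, and I do not recommend it.

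**Conclusion.** The point holds in limited form. As the protocol is worded, inclusion of signs and symptoms depends on outcome, in a way that neither the section's opening definition nor its Reactions list does. The Signs and Symptoms Grade 5 cell is empty on a literal reading. The Grade 3 or higher and Grade 4 or higher rows, there and in the overall IRR line, can be undercounted. The direction is downward. The size cannot be estimated from the documents and is probably small in number of events, but in groups as small as those assumed above one event decides whether a row is zero.

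This assumes that the redacted Appendix 1 Table 1 carries the protocol rule over unchanged and that a fatal outcome is treated as unresolved. If the appendix already handles long or fatal events differently, the point falls away or shrinks.

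**What to change.** Keep the current definition as the main IRR analysis. Add to SAP Section 15.3.3 one supplementary row or flagged listing, by worst grade, of the listed signs-and-symptoms terms with onset during or within 1 day after an infusion, irrespective of duration or outcome. Confirm at the same time that Appendix 1 Table 1 says how ongoing and fatal events are treated under the resolution condition.

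The cost is one sentence in the SAP and one programming condition, with no new data and no change to clinical management. The drawback is that some disease-related events, such as dyspnea or back pain starting near an infusion, will appear in the added output. It should therefore be labelled as supplementary and not be read as a count of confirmed IRRs.

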8.3.6.2 Immune-related Adverse Events

Immune-related AEs are specific to immunotherapies and vary by organ system. Immune-related AEs are AESIs.

The following irAEs are important identified risks for bintrafusp alfa.

- Immune-related pneumonitis
- Immune-related hepatitis
- Immune-related colitis
- Immune-related nephritis and renal dysfunction
- Immune-related endocrinopathies (thyroid disorders, adrenal insufficiency, Type 1 diabetes mellitus, pituitary disorders)
- Immune-related rash
- Other immune-related events (myositis, myocarditis, encephalitis).

The following irAEs are important potential risks for bintrafusp alfa:

- Guillain-Barré syndrome
- Uveitis
- Pancreatitis
- Myasthenia gravis/myasthenic syndrome.

In general, the spectrum of irAEs is similar for bintrafusp alfa compared with other checkpoint inhibitors. Effective risk management of these toxicities (irAEs) primarily caused due to inhibition of PD-L1 and PD-1 pathways is based on key recommendations ([Champiat 2016](#)). Participant education for on-time reporting of symptoms of potential irAEs and prompt clinical assessment is critical for effective management and quicker resolution of immune-mediated toxicities, thus preventing progression into severe forms of toxicity that otherwise may become life-threatening and difficult to manage or warrant permanent discontinuation from the study.

The Medical Monitor may be involved as needed for Follow-up. Details of the diagnostic work-up will be requested by the study team.

Recommended guidance and management for specific irAEs are provided in the current NCCN guideline is available at <http://www.nccn.org>

Requirements in addition to NCCN guidelines:

- Permanent treatment discontinuation is required in case of immune-related Grade 4 rash/inflammatory dermatitis, nephritis, autoimmune hemolytic anemia, hemolytic uremic syndrome, aplastic anemia, immune thrombocytopenia, acquired thrombotic thrombocytopenic purpura, inflammatory arthritis, myositis, and polymyalgia-like syndrome.
- For Grade 4 immune-related lymphopenia, permanent treatment discontinuation will be required, if lymphopenia is considered immune-related in nature, no clear alternative explanation exists for the event, and Grade 4 lymphopenia does not resolve within 14 days. Permanent treatment discontinuation is not required when the AE is manifest by a single laboratory value out of normal range without any clinical correlates. In this case, treatment should be held until the etiology is determined. If the event is not considered immune related and resolves to Grade ≤ 1 , restarting treatment may be considered.
- For Grade 1 immune-related pneumonitis: continue treatment. If clinically indicated, monitor participants weekly or more frequently as needed with history, physical examination, and pulse oximetry. If symptoms appear and/or changes in the physical examination are noted, treat as Grade 2.
- For myositis: in case of management with rituximab, treatment should be discontinued.

8.3.6.3 TGF β inhibition mediated Skin Reactions

Skin assessments will be performed for all participants per the SoA (see Table 1). For participants who are reinitiating treatment with bintrafusp alfa after treatment discontinuation within the rollover study, a rebaseline skin assessment should also be performed.

Skin AEs, possibly due to TGF β inhibition, including hyperkeratosis, KA, and/or cSCC, are AESIs and important identified risks for bintrafusp alfa. The distribution of lesions tends to be in sun-exposed areas.

Management guidelines for potential TGF β inhibition mediated skin reactions are:

1. Discontinuation or interruption is not required in most cases. Continuation of treatment should be evaluated by the Investigator.
2. Emollients may continue to be used.
3. Diagnostic and treatment plan should be developed in collaboration between Investigator and dermatologist. In general, treatment of TGF β mediated skin lesions such as hyperkeratosis, KA and cSCC should be based on local guidelines/SoC. Lesion evaluation should include excision biopsy of one representative lesion to confirm diagnosis.

4. Treatment and Follow-up for KA and cSCC will depend on number and localization of lesions.
 - For single lesions: Full excision may be recommended.
 - In case of multiple lesions or location not suitable for full excision, other treatment options may be offered by the dermatologist, such as:
 - Mohs surgery, cryotherapy, or other standard treatment options depending on the pathology,
 - Use of retinoids, if recommended by dermatologist, may be considered after discussion with Medical Monitor.
5. Close clinical Follow-up for re-evaluation, resolution, or potential recurrence should be implemented.
6. Spontaneous resolution of KA lesions without surgical intervention has been observed, typically occurring within weeks after discontinuing bintrafusp alfa.
7. The number and localization of lesions, diagnosis (including histopathological diagnosis), treatment, and outcome should be appropriately documented in the eCRF.

Consult with study Medical Monitor, as needed, for management of TGF β mediated skin lesions.

